#### 5.71 Reporting Adverse or Unanticipated Events

The Investigator will ensure that all adverse events AEs that occur during the study period are well documented and reported timely to the IRB.

Documentation of AEs includes: date and time of onset and resolution of AE, intensity, frequency, seriousness, related interventions, and outcome. The Investigator will also evaluate the probability of a causal relationship of the AE to the study intervention as being: “definite, probable, possible, unlikely, or unrelated.” Intensity of adverse events will be graded as mild, moderate, or severe according to the following criteria:

Mild: symptoms that are easily tolerated and transient in nature with minimal or no impairment of normal activity

Moderate: symptoms that are poorly tolerated, are sustained, and interfere with normal activity

Severe: symptoms that are incapacitating and render the subject unable to work or participate in many or all usual activities

All AEs will be reported to the IRB according to the IRB’s requirements, regardless of causality.

#### 5.72 Anticipated Reactions

We do not anticipate any adverse reaction consequent to participating in this study. This study is not invasive and does not prescribe medications nor recommend new treatment protocols. The iThermonitor only helps to timely detect the onset of out-of-range temperature. Participants will be advised to contact their physicians if they experience any problems with their medications or medical illness

#### 5.73 Reaction Management

Should an AE be encountered, the first step in the process, after any actions required for patient stabilization, will be to record the event on the adverse event reporting log and also notify the principal investigator. The event will be classified base on the relatedness, severity and whether it is an anticipated or not. The AE will be reported and managed based on relatedness to the use of the iThermonitor, seriousness and whether it was anticipated or unanticipated. The principal investigator will in turn notify the IRB and the subject’s physician. All AEs will be monitored until resolution

or until, in the investigator's judgment, they are stable. If an emergency situation should occur, appropriate medical emergency measures should be taken to stabilize the subject.

## 6.0 Statistical Analysis

This study will be implemented as a pilot study to evaluate the use feasibility of the iThermonitor as a clinical decision support tool for continuous temperature monitoring in a dyad of 25 pediatrics patients (aged 2-17yrs) on myelosuppressive therapies for acute leukemia and other childhood cancers at the MGH Cancer Center and their caregivers over a 2-week study period.

### 6.1 Primary and secondary endpoints

6.1a Primary outcome measurement: use feasibility of the iThermonitor will be assessed by ability of the device to successfully capture, transmit and display the patient's body temperature data on the study iPad mini. To limit recall bias, subjects will be required to log (Appendix 5) the ability to view the temperature data on the iPad mini once a day for the entire duration of the study. The device will be deemed a feasible continuous temperature monitoring tool if at least 80% of study subjects are able to successfully use the iThermonitor to monitor their body temperature. A subject must be able to view temperature data on the provided iPad mini at least 80% of the time in the study to be considered successful. "Time in the study" here is defined as the number of days the subject spends in the study which is expected to be two weeks.

6.1b Secondary outcomes: secondary outcomes which will be assessed at the end of the study include:

- i. Usability, acceptability and satisfaction with the iThermonitor. This will be assessed by questionnaires specifically designed for this study. We will be assessing ease of use, acceptability, connection and use problems like the device falling off the skin, usefulness of out-of-range temperature alerts and adverse reactions. We will also assess to see if the device helps to build caregiver self-efficacy skills in caring for the patient.
- ii. Caregiver engagement with the iThermonitor. This will be assessed by time to first measurement and upload from the time of discharge and also by the frequency of logins to the iThermonitor app.
- iii. Caregiver anxiety will be assessed using the GAD-7 questionnaire.

6.2 Sample size and statistical power or precision associated with the sample size: The length of time required to accrue an adequate number of subjects to the study should be indicated.

We will be able to estimate a feasibility success rate of 80% to within a 95% confidence interval of +/- 16% with a sample size of 25 evaluable patients. This is in keeping with a

recommendation of sample size of at least 24 subjects for feasibility studies. Therefore, a dyad of 25 pediatric patients and their caregivers will be enrolled in the study. Based on estimates from the Partners Healthcare Research Patient Data Registry, about 101 pediatric patients with hematologic malignancies alone were seen in 2013 at the MGH Cancer Center. We envisage that we would be able to accrue enough subjects over 12 months after the enrollment of the first subject.

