#### 5.4 Data Collection

- The use feasibility data will be collected by a daily event monitoring log designed specifically for this study which will be recorded manually by subjects everyday throughout the study period.
- Data collected by the iThermonitor is automatically uploaded to a paired receiver within a range of five meters for cloud storage. These data will be downloaded on a weekly basis and stored in the Partners Healthcare network of computer files available to only the IRB approved study staff at the Partners Connected Health Innovation. Partners Connected Health Innovation is an established leader in the creation and implementation of effective healthcare delivery strategies supported by patient-centric technology. At PCHI, we leverage information technology – mobile phones and apps, remote monitoring tools, personal health trackers, sensors, computers and networked devices – to help providers and patients manage chronic conditions, maintain health and wellness, and improve adherence, engagement and clinical outcomes.
- We will collect information about the participant’s type of cancer, stage of disease and treatment regimens from a review of the electronic medical records.
- Enrollment, usability and satisfaction data will be collected by questionnaires designed specifically for this study.

Outcome data will be stored in computer network files that are accessible only to IRB approved study staff. Outcome data will be linked to each subject by a unique number, which will not have any identifying information. All data collected will be analyzed at the end of the study period.

A summary of data points to be assessed in this study is summarized in the table below:

Assessments	At entry	During the study	Close out (+/- 5days)
Enrollment questionnaires	X		
Temperature measurements via device	X	X	
Daily event monitoring log		X	X

Number of out-of-range temperature episodes detected		X	
Usability and satisfaction questionnaires and other closeout surveys			X
GAD-7	X		X

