#### 5 Wearing

Step 1. Lift the arm naturally.

Step 2. P

Note: An adult should help children wear and operate the device, to ensure the area of skin it is in contact with stays flat and smooth.

Note: To avoid disconnections, please make sure device and receiver are on the same side of your chest when wearing the device.

[figure not shown]
- If the connection is lost, the sensor will continue recording and storing temperature data for maximum 10 days. The data will be automatically synced with iPad once the connection is back.

[figure not shown]

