**4. How often did you view the measurements? (Please circle one of these options)**

- a. Hourly
- b. 2-hourly
- c. 4-hourly
- d. Daily
- e. 2-3 times per week
- f. Once a week
- g. never
- h. other: \_\_\_\_\_

**5. Was viewing measurements on the app useful in being able to better manage your child's health? (Please circle one of these options)**

- a. Yes
- b. No
- c. Prefer not to answer

**6. Did viewing measurements on the app help you become more interested in your child's health? (Please circle one of these options)**

- a. Yes
- b. No
- c. Prefer not to answer

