### iThermonitor Daily Event Monitoring Log

Please indicate **Yes** or **No** for each column everyday during the study.

Day	The iThermonitor stayed on the body for most of the day		I was able to view the temperature data on the iPad mini	
	Yes	No	Yes	No
1				
2				
3				
4				
5				
6				
7				
8				
9				
10				
11				
12				
13				
14				

Caregiver Signature \_\_\_\_\_ Date \_\_\_\_\_

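### The daily log has no 'did not look' answer and no scoring rule for such days, so the primary rate mixes device display with caregiver viewing and can be biased in either direction

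*Combined protocol and SAP*

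**What the plan says.** Section 6.1a states the primary outcome as a property of the device: "ability of the device to successfully capture, transmit and display the patient's body temperature data on the study iPad mini". The measurement is a diary entry: "subjects will be required to log (Appendix 5) the ability to view the temperature data on the iPad mini once a day". Section 5.4 confirms the source: "The use feasibility data will be collected by a daily event monitoring log designed specifically for this study".

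The log in Appendix 5.2 has two Yes/No columns for each of 14 days. One concerns wear: "The iThermonitor stayed on the body for most of the day". The other feeds the primary outcome: "I was able to view the temperature data on the iPad mini". There is no answer for a day on which the caregiver did not look, and no place to give a reason for a No.

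The subject-level threshold in 6.1a is: "A subject must be able to view temperature data on the provided iPad mini at least 80% of the time in the study". At study level, 6.1a calls the device feasible if at least 80% of subjects succeed. Section 6.7 calls it not feasible if the upper 95% limit is below 80%. Section 6.8 specifies a complete case analysis and does not mention blank days within a subject.

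Three other places bear on the point. Question 4 of the close-out survey (Appendix 4.1) asks "How often did you view the measurements" and includes answers well below daily. Section 6.1b makes caregiver engagement a separate secondary outcome. The instruction guide (Appendix 1.4) says of a lost connection: "The data will be automatically synced with iPad once the connection is back".

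**The concern.** On a day when the caregiver did not open the app on the iPad mini, the log item has no clearly correct answer, and each possible answer means something different for the endpoint.

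- **No** records a day against the device although it may have worked.
- **Yes** may hide a day on which nothing was displayed. It may also reflect older readings that synced later, because the item does not ask for a reading from that day.
- **Blank** has no stated effect on the numerator or denominator of the 80% rule.

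The wear column does not resolve this, because a child can wear the sensor all day while nobody looks. Section 5.3 also lets caregivers view the data on their own phone or tablet, so the study iPad mini can go unopened while the system works.

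At stake is what the primary result means. A rate below 80% could come from a device that failed to display or from caregivers who did not look. A rate above 80% could contain unseen display failures. The primary analysis as planned cannot tell these apart.

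**Working it through.** **The plan's own figure.** Section 6.2 gives ±16% around 80% with 25 evaluable patients. The normal-approximation half-width is 1.96 × √(0.8 × 0.2 / 25) = 0.157, which rounds to 16%, so the figure reproduces.

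**Thresholds.**
- Subject success: 0.80 × 14 = 11.2, so 12 of 14 Yes days. Three No days fail a subject.
- Study, 6.1a: 0.80 × 25 = 20 of 25 subjects.
- Study, 6.7: the exact upper 95% limit is 78.9% at 15/25 and 82.0% at 16/25, so 'not feasible' means 15 or fewer. The normal approximation gives the same cut; the Wilson interval gives 16 or fewer. Section 6.7 does not name the interval.

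**Unlooked days ticked No.** The looking rate q is not in the documents, so a range is assumed. Other assumptions: the device displays every day, every unlooked day is ticked No, days are independent, and all caregivers share one q. Then:

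- subject success s = P(X ≥ 12), X ~ Binomial(14, q). At q = 0.90: 91 × 0.9¹² × 0.1² + 14 × 0.9¹³ × 0.1 + 0.9¹⁴ = 0.257 + 0.356 + 0.229 = 0.842;
- study results from Y ~ Binomial(25, s).

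| q | s | P(Y ≥ 20) | P(Y ≤ 15) |
|---|---|---|---|
| 95% | 97.0% | >99% | <1% |
| 90% | 84.2% | 80.6% | 0.3% |
| 85% | 64.8% | 7.9% | 37.8% |
| 80% | 44.8% | <1% | 95.8% |

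With the Wilson cut of 16, the last column at 90/85/80% becomes 1.1/54.2/98.3%.

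**Uneven looking.** Suppose 20% of caregivers look on 70% of days (s = 0.161 for them) and the rest look daily. Then s = 0.80 + 0.20 × 0.161 = 0.832. The chance of fewer than 20/25 is 23.3%, and of 15 or fewer 0.5%.

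**Unlooked days ticked Yes.** With a device that always displays, the effect is zero. With a device that does not, it flatters. If nothing is shown on 4 of 14 days, true display is 10/14 = 71%, below the threshold. If the caregiver did not look on two of those four days and ticked Yes, the log shows 12/14 = 86% and the subject succeeds.

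**Unlooked days left blank.** If blanks are dropped from the denominator, a device that always displays scores 100% whatever q is. If blanks stay in a denominator of 14, the result is the same as ticking No. The plan does not say which applies.

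**The case against.** **Non-viewing may be meant to count.** The endpoint is called use feasibility, sections 2.1 and 6.1a ask whether subjects can successfully use the device, and the justification of the inclusion criteria expects caregivers to monitor the iPad mini. This stands as a reason to let unlooked days count against use feasibility. It does not supply the missing rule, and it does not fit the sentence in 6.1a that defines the outcome by what the device does.

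**Other data are collected.** Readings are uploaded and downloaded weekly (5.4), login frequency is recorded (6.1b), and the close-out survey asks about viewing and problems. A reader might infer that nothing collected could separate the two causes; that goes too far. The evidence is partial, though. Uploads bear on capture and transmission, but the sensor stores up to 10 days of readings and syncs later, so they do not show what was displayed on a given day. Logins are a weak marker of looking, because the guide tells families to stay logged in. None of these sources enters the primary analysis in 6.7.

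**Unlooked days may be rare.** The low options in the close-out question are a response list, not a forecast, and completing a daily log itself prompts a look. This stands, and it is why the looking rate must be treated as unknown.

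**The stronger reading.** A reader might infer that the plan scores non-looking as device failure, so that a working device will be called not feasible. No section says so. No is one of three possible responses, and the other two remove or reverse the effect.

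**Conclusion.** The concern holds in this form: the log cannot separate a device that showed nothing from a caregiver who did not look, no rule covers such days, and the primary analysis draws on nothing else to tell them apart. The direction of the bias is not fixed.

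The size cannot be stated from the documents. If unlooked days are ticked No, the effect is negligible when caregivers look on 95% of days. At 90% it gives about a one-in-five chance of missing 20/25 with a device that always displays, and at 85% or below missing that target becomes the likely result. The 6.7 'not feasible' rule is much less sensitive: under the exact interval it is hardly affected at 90% looking and seriously affected at 85% or below. These figures rest on independent days and a common looking rate, and illustrate one of the three ways of marking. The change is worth making because it is cheap and because an unlooked day cannot be reliably identified after the fact.

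**What to change.** 1. **Appendix 5.2.** Replace the second column with three boxes per day, referring to the study iPad mini: 'Looked: a reading from today was shown', 'Looked: no reading from today was shown', 'Did not look today'.
2. **Sections 6.1a and 6.7, primary rate.** Keep the 80%/80% use-feasibility rule and state that 'did not look' days count as not viewed.
3. **Section 6.7, display rate.** Beside the primary rate, report a device-display rate with only looked days in the denominator, summarised like the primary rate (per subject, then the share of assessable subjects reaching 80%). Give the number of looked days per subject. Report subjects with no looked days as not assessable for display, not as successes. The denominator matters: if unlooked days counted as display successes, a caregiver who looked twice and saw nothing would score 12/14 = 86%, and one who never looked would score 100%.
4. **Section 6.7, uploads.** From the weekly downloads, report the share of days with uploaded readings as supporting evidence on capture and transmission.
5. **Interpretation.** Attribute a primary result below 80% to the device only if the looked-days display rate is also below 80%. Otherwise describe it as limited caregiver viewing.

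The cost is one more box on a one-page form, slightly more for caregivers to read each day, and two extra descriptive proportions. The sample size and the decision thresholds do not change.

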## **2.0 Objectives**

### **2.1 Hypothesis**

We hypothesize that at least 80% of study subjects will be able to successfully use the iThermonitor to continuously monitor their body temperature. A subject must be able to view temperature data on the provided iPad mini at least 80% of the time in the study to be considered successful. "Time in the study" here is defined as the number of days the subject spends in the study which is expected to be 14 days.

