## 2.2 Primary and Secondary aims:

2.21 The primary aim of this trial is to assess the use feasibility of the iThermonitor as a clinical decision support tool in the management of patients on myelosuppressive therapies for acute leukemia and other childhood cancers. We will consider the iThermonitor as a feasible clinical decision support tool if it successfully captures body temperature data, transmit and displays the data on the iPad mini in at least 80% of the study subjects. We will also assess the ability of the device to alert the caregiver if the temperature falls outside of pre-set range which is defined for all patients as temperature less than or equal to 96 and greater than or equal to 100.

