#### ***Registration Process for DF/HCC and DF/PCC Institutions***

The QACT registration staff is accessible on Monday through Friday, from 8:00 AM to 5:00 PM Eastern Standard Time.

The registration procedures are as follows:

- Obtain written informed consent from the participant prior to the performance of any protocol specific procedures or assessments.
- Complete the QACT protocol-specific eligibility checklist using the eligibility assessment documented in the participant's medical record and/or research chart. **To be eligible for registration to the protocol, the participant must meet all inclusion and exclusion criterion as described in the protocol and reflected on the eligibility checklist.**
- Fax the eligibility checklist(s) and all pages of the consent form(s) to the QACT at [contact]. For Phase I protocols, attach participant dose level assignment confirmation from the sponsor.
- The QACT Registrar will (a) review the eligibility checklist, (b) register the participant on the protocol, and (c) randomize the participant when applicable.
- An email confirmation of the registration and/or randomization will be sent to the Overall PI, study coordinator(s) from the Lead Site, treating investigator and registering person immediately following the registration and/or randomization.

5.63 During the study:

- If the study team does not receive data from the iThermonitor by the second day after study enrollment, study staff will follow-up (telephone call) with subjects to ensure that they are able to correctly set-up the device. We will encourage participants to continue to receive medical treatment and adhere to other management protocols as recommended by their physicians as usual. We will emphasize that the iThermonitor does not replace usual temperature monitoring protocols.
- Use the iThermonitor everyday to monitor the patient's temperature continuously until final study closeout.
- Complete the event monitoring log every day.
- In the event of a hospital admission during the study period, the hospitalized subject will stop using the device. If the subject has contributed less than 50% of data (i.e. used the device for less than 7 days) prior to hospitalization, they will be dropped from the study and another subject will be recruited to make up the enrollment

target. However, subjects who have contributed at least 50% of data prior to hospitalization will stop using the device but will be included in final analyses.

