### 6.7 Analysis plan

Data collected will be verified before analysis, which will be done with Data Analysis and Statistical Software: STATA, version 13 with an alpha of 0.05 set a priori. All participants will be followed up for two weeks and we will summarize their baseline demographic and technology use characteristics.

To address the primary aim, the feasibility success rate will be calculated as the number of evaluable patients who meet the criteria for 'success' (per section 6.1) divided by the total number of evaluable patients. A 95% confidence interval will be calculated on this proportion. If the upper limit of the 95% confidence interval is less than 80%, then we will consider the iThermonitor not to be a feasible clinical decision support tool.

Descriptive analyses will be performed on all baseline data. Endpoints for all study outcomes are defined in section 6.1 above. All continuous variables will be computed as means with standard deviations, median and ranges while categorical variables will be computed as frequency distributions and percentages. The binomial test of proportion will be used to our dichotomous outcome of successfully using the iThermonitor. Paired t-test will be used to

analyze pre- and post- GAD-7 scores measured as a continuous variable. All other outcome variables will be summarized with descriptive statistics.

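### A 'continuous monitoring' verdict rests on a daily yes/no about viewing data: no endpoint uses the log's wear column, and the receiver rules need reconciling

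*Combined protocol and SAP*

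**What the plan says.** **The success rule.** Section 2.1 hypothesises that at least 80% of subjects can "successfully use the iThermonitor to continuously monitor their body temperature". Section 2.21 calls the device feasible if it captures, transmits and "displays the data on the iPad mini in at least 80% of the study subjects". Section 6.1a sets the subject-level rule: "A subject must be able to view temperature data on the provided iPad mini at least 80% of the time in the study". Time is counted in days, 14 expected, and the caregiver logs ability to view once a day. If at least 80% of subjects succeed, "The device will be deemed a feasible continuous temperature monitoring tool". Section 5.63 asks families to use the device every day to monitor "temperature continuously until final study closeout".

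**The analysis.** Section 6.7 divides successes by evaluable patients and gives a 95% confidence interval. It states that "Endpoints for all study outcomes are defined in section 6.1 above". Its negative rule begins "If the upper limit of the 95% confidence interval is less than 80" (per cent); in that case the device is considered not feasible. Outcome variables not otherwise assigned a test are summarised descriptively.

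**Wear.** The log (Appendix 5.2) has two daily yes/no columns: whether the device stayed on for most of the day, and whether data could be viewed on the iPad mini. Section 5.4 says the log collects the use feasibility data. Section 6.1 does not mention the wear column. Secondary outcome i covers "connection and use problems like the device falling off the skin", but by questionnaire (Appendix 4.1, item 11 and question 13a).

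**The receiver.** Section 5.3 says staff will install the app on a caregiver's own device if the caregiver prefers it, and the letter to oncologists (Appendix 2.1) names an iPad mini or a smartphone. The justification of inclusion criteria (3.1b) requires caregivers to monitor on the provided iPad mini. A later paragraph of 5.3 and section 5.61 make an own phone additional. Section 5.68 ties each dyad's payment to return of the iPad mini.

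**The concern.** **Wear.** The conclusion uses the word continuous, but a day counts on a single yes/no about being able to see data. A day of brief wear on which data were seen can count in full, because the rule sets no minimum wear and no minimum completeness. The log column that speaks to this every day has no assigned role in the verdict. The close-out questions on wear rely on recall at the end of the study, although 6.1a chose daily logging to limit recall bias. A combined wear-and-view rate that is first devised after the data are in would be post hoc.

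**The receiver.** If an own device may replace the iPad mini, the rule and the log column can score a family as a failure when the sensor captured, transmitted and displayed data throughout. With 25 subjects, a few such families would move the rate for a reason unrelated to whether the device works.

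**Working it through.** **1. The plan's own figure.** Section 6.2 gives 80% ± 16% with 25 evaluable patients. The normal approximation gives 1.96 × √(0.8 × 0.2 / 25) = 0.157, which rounds to 16%, so the figure reproduces. The sample-size arithmetic is not in question.

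**2. Thresholds.**
- Subject: 0.8 × 14 = 11.2, so 12 view-days of 14.
- Study: 0.8 × 25 = 20 successes.
- Negative rule in 6.7, upper 95% limit: at 15/25 it is 79.2% (Wald), 78.9% (exact) or 76.6% (Wilson). At 16/25 it is 82.8%, 82.0% or 79.75%. The rule therefore triggers at 15 or fewer by Wald or exact, and at 16 or fewer by Wilson. Section 6.7 does not name the interval method.

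**3. What a view-day guarantees.** Section 5.3 gives one reading every four seconds, so 86,400 / 4 = 21,600 possible readings a day. Twelve 'Yes' marks are a success whatever share of these was captured.

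**4. How far viewing and wear could diverge (illustration only).** The documents give no wear rate, so every input here is an assumption. Data are viewable on 95% of days, and the sensor is worn most of the day on 100%, 95% or 90% of those days. The chance that both columns are 'Yes' is then 0.95, 0.9025 or 0.855. With independent days, subject success is P(X ≥ 12), X ~ Bin(14, p). With within-child correlation r it is beta-binomial, a = p(1−r)/r and b = (1−p)(1−r)/r.

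| Correlation r | View only (same as 100% wear) | Both columns, 95% wear | Both columns, 90% wear |
|---|---|---|---|
| 0 | 97% | 85% | 67% |
| 0.1 | 91% | 80% | 67% |
| 0.3 | 90% | 81% | 71% |
| 0.5 | 91% | 83% | 75% |

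The gap from view-only runs from 0 (full wear) to 30 points (90% wear, independent days). Correlation narrows it without removing it.

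At study level with 90% wear, the chance of at least 20/25 on both columns is 0.12 at subject success 0.668 (r = 0) and 0.23 at 0.711 (r = 0.3). The chance of more than 15/25, which would not trigger the 6.7 rule by Wald or exact, is about 0.70 and 0.84.

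**5. Own-device families.** Each one who would otherwise succeed costs 1/25 = 4 points. If all others succeed:
- five leave 20/25 = 80%, which still meets the target;
- six leave 19/25 = 76%, below it;
- nine leave 16/25 = 64%, which triggers the 6.7 rule by Wilson;
- ten leave 15/25 = 60%, which triggers it by Wald or exact as well.

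**The case against.** The best defence is that the endpoint was chosen deliberately and stated consistently. Sections 2.1, 2.21 and 6.1a all score success by data reaching the iPad mini, and viewing is the last link in that chain. 'Continuous' describes how the device works, and no section promises a wear-time endpoint. This is a 25-dyad pilot. That stands: the view-based rate is a valid primary for the aim as written.

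The plan does not ignore wear either. Section 5.4 assigns the whole log to use feasibility, 6.7 would plausibly summarise the wear column descriptively, and detachment is a stated secondary topic. This narrows the gap, but a collection statement does not define an endpoint, and nothing links wear to the verdict. Also, 'once a day' in 6.1a can be read as how often the log is filled in. The item asks about ability to view, not whether the caregiver looked only once. A single look would satisfy it, but that is not what it sets out to measure.

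On the receiver, section 5.3 never says the iPad mini is withheld, and 3.1b, 5.61 and 5.68 point to every dyad holding and using one. A reader might infer from the reminder letter (Appendix 3.2), which mentions a study-provided iPod Touch, that only some families had a study receiver. The protocol body names no such device, and the line looks like leftover text. It is not good evidence of a replacement policy. What remains is wording in 5.3 and Appendix 2.1 that can be read either way.

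**Conclusion.** The concern holds in a limited form. A daily view report supports the statement that data could be captured, transmitted and displayed. By itself it does not support the statement that the child was monitored for most of the day. The daily wear column would at most be summarised descriptively and enters no endpoint in 6.1. The receiver passages need reconciling, because the literal rule fails a family that views only on its own device.

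A reader might go further and infer that the primary rate is wrong, that the trial will probably miss its target, or that own-device replacement is settled policy. The documents support none of these. They give no wear rate and no own-device share. The wear and correlation scenarios are assumptions, and the 6.7 negative rule needs a result as low as 15/25 (16/25 by Wilson). The one firm quantity is 4 points per own-device-only subject who would otherwise succeed, and it matters only if such subjects occur. Priority is minor to moderate.

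**What to change.** **(a) Receiver.** Reconcile section 5.3 and Appendix 2.1 with 3.1b (justification), the later paragraph of 5.3, 5.61 and 5.68, and correct the iPod Touch wording in Appendix 3.2. If an own device may replace the iPad mini, word the success rule (2.1, 2.21, 6.1a) and the log's viewing column as the study iPad mini or any paired receiver. If not, state in 5.3 that the iPad mini must be used.

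**(b) Wear.** Keep the view-based primary and the 6.7 rule unchanged. Pre-specify in 6.1 and 6.7 one supporting rate: the proportion of evaluable subjects with both log columns 'Yes' on at least 80% of their study days, with a 95% confidence interval by the same method as the primary. State that the primary alone supports only capture, transmission and display. State also that any conclusion about continuous monitoring must be qualified by the supporting rate, for example not made without qualification if that rate is below 80%.

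**Cost.** Wording changes and one extra rate, with no new data source and no change in sample size. The downsides are slightly more analysis, a wear measure that is self-reported, and a supporting figure that may be less favourable than the primary. The last is a reason to let it support the primary rather than replace it.
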